9.1.10. Patient Assessment of GI Disorders Severity Quality of Life (PAGI-QoL)

The PAGI-QoL assesses the effect that GI problems have on daily life over the past 2 weeks. There are 30 items which are rated from 0 (none of the time) to 5 (all the time).

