## 3.2 SECONDARY EFFICACY ENDPOINTS

The Movement Disorder Society - Unified Parkinson's Disease Rating Scale (MDS-

UPDRS) is used for several of the endpoints below. It is a four-part scale, with each item in the scale rated as 0-4, where 0=normal, 1 = slight, 2 = mild, 3 = moderate, and 4 = severe.

Change from baseline is calculated for each endpoint as *Value at Visit X - Value at baseline*.

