### 3.2.9 Complete Spontaneous Bowel Movement Score (CSBM)

The mean number of complete spontaneous bowel movements (CSBM) during the previous week will be assessed at baseline and at each Visit. A “spontaneous” bowel movement is a stool not induced by rescue medication such as laxative, enema, or suppository use during the previous 24 hour period. “Complete” refers to the sensation of complete evacuation of the stool.

Constipation is defined by the Rome IV criteria for constipation as less than or equal to 3 spontaneous bowel movements per week.

CFB will be calculated as the sum of unassisted diary values for Visits 2 (Week 4), 3 (Week 8), and 4 (Week 12). An increase (positive value) reflects improvement.

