### **3.2.11 Schwab and England Activities of Daily Living Scale (SE-ADL)**

The SE-ADL is a single item that assesses the difficulty that a participant has in completing daily activities. It ranges from 0% (bedridden) to 100% (completely independent). Scores are coded in increments of 10 (i.e., 100, 90, 80, ...). CFB will be calculated for Visits 2 (Week 4), 3 (Week 8), 4 (Week 12), and 5 (Safety follow-up). The participant value will be recorded. A positive value of CFB reflects improvement.

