### 3.2.14 Patient Assessment of GI Disorders Severity Quality of Life (PAGI-QoL)

The Patient Assessment of GI Disorders Severity Quality of Life (PAGI-QoL) assesses the effect that GI problems have on daily life over the past 2 weeks. There are 30 items in 5 dimensions: daily activities (10 items, Q1-10), clothing (2 items, Q11-12), diet and food habits (7 items, Q13-20), relationship (3 items, Q20-22), and psychological well-being and distress (8 items, Q23-30). Each item is rated from 0 (none of the time) to 5 (all the time) ([De La Loge et al, 2004](#)).

Individual items are rated such that a higher score represents a worse outcome. However, each subscale score is taken as the mean of the items in each subscale, when all item responses are reverse-coded such that a higher score represents a better disease-specific quality of life. The PAGI-QOL summary score is calculated as the mean of all subscales ([Sebaratnam et al. 2021](#)).

In case of missing data, the subscale score is calculated when 50% or less of the items are missing for that scale. If >50% of items in a subscale are missing, the score is set to missing. If a subscale score is set to missing then the total score is also set to missing.

CFB will be calculated for Visits 2 (Week 4), 3 (Week 8), and 4 (Week 12). A negative CFB reflects improvement.

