## 4.2.3 Secondary Efficacy Analyses

The efficacy endpoints (as changes from baseline at Week 12) will be evaluated in hierarchical order as described in [Section 2.4](#). The following endpoints will be evaluated:

- Movement Disorder Society-sponsored revision of the Unified Parkinson's Disease Rating Scale (MDS-UPDRS) Parts II + III
- Parkinson's Disease Questionnaire (PDQ-39) summary index
- Patient Global Impression-Severity (PGI-S)
- Clinician Global Impression of Severity (CGI-S)
- MDS-UPDRS Part II
- MDS-UPDRS Part III
- MDS-UPDRS Part I
- Non-Motor Symptom Scale (NMSS) total score
- Complete Spontaneous Bowel Movement Score (CSBM)
- Epworth Sleepiness Scale (ESS) total score
- Schwab and England Activities of Daily Living (SE-ADL) Scale
- Patient Assessment of Upper Gastrointestinal Disorders Severity Index (PAGI-SYM)
- Patient Assessment of Constipation Quality of Life (PAC-QoL)
- Patient Assessment of Gastrointestinal Disorders Severity Quality of Life (PAGI-QoL)

The estimand for the key efficacy endpoint is defined as follows:

- A. Population: Participants with Parkinson's Disease as defined by inclusion/exclusion criteria and in the modified Intent-to-Treat (mITT) population.
- B. Variable: Change from baseline to Week 12 in the MDS-UPDRS Parts II + III score.
- C. Intercurrent Events:
  - a. Premature Discontinuation of Study Treatment
  - b. Initiation of PD Medication for Treatment of Motor Features
- D. Summary: Treatment differences of the least-squared mean (LSM) change from baseline at Week 12 in the MDS-UPDRS Parts II + III summary index between 50, 100, or 200 mg IKT-148009 vs placebo.

For data that are missing due to premature discontinuation of study treatment or initiation of PD medication, no specific imputation will be done. If possible, the collection of data will be continued and used according to the treatment policy strategy. Descriptive statistics for each endpoint will be presented as change from baseline by treatment group and visit.

The differences between the dose levels versus placebo at Week 12 in the continuous secondary endpoints will be estimated using a Mixed Model for Repeated Measures (MMRM) using the mITT Set.

For each endpoint and treatment group, the null hypothesis will be  $H_0: \delta = 0$  and the alternative hypothesis will be  $H_0: \delta \neq 0$ , where  $\delta$  = treatment difference =  $(\bar{x} - \mu)$ .

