For participants  $i=1, \dots, I$  and repeated observations  $j=1, \dots, J$ , the MMRM model can be parameterized as

$$\mathbf{Y}_i = \mathbf{X}_i \boldsymbol{\beta} + \mathbf{Z}_i \mathbf{b}_i + \boldsymbol{\epsilon}_i$$

Where  $\mathbf{Y}_i$  = a  $J_i$  dimensional vector of outcome measurements for the  $i^{\text{th}}$  participant,

$\boldsymbol{\beta}$  = a  $p$  dimensional vector containing the fixed effects (baseline, treatment effect, time),

$\mathbf{X}_i, \mathbf{Z}_i = (J_i \times p)$  and  $(J_i \times q)$  dimensional design matrices of known covariates,

$\mathbf{b}_i = q$  dimensional vector containing the random effects ( $\mathbf{b}_i \sim N(0, D)$ ) and

$\boldsymbol{\epsilon}_i = J_i$  dimensional vector of residual components ( $\boldsymbol{\epsilon}_i \sim N(0, \Sigma_i)$ ).

The MMRM will include the observed change from baseline from Week 4, Week 8, and Week 12 as the response values, baseline value as a covariate, and treatment group, visit, and treatment group  $\times$  visit interaction term as fixed factors. An unstructured covariance structure will be assumed first. If this model does not converge, Heterogeneous Autoregressive (1) (ARH[1]), Heterogeneous Compound Symmetry (CSH), Autoregressive (1) (AR[1]) or Compound Symmetry (CS) covariance structure will be used (in this order). The denominator degrees of freedom will be computed using the Kenward-Roger method.

The least square (LS) means estimate for each treatment group, SEM, and LS mean difference between different dose levels and placebo will be provided, along with the 95% confidence intervals (CI) and  $p$ -value, for each assessment. Only the LS means for Week 12 will be used for statistical comparison.

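### The SAP scores PAGI-QoL so that higher is better, but calls a negative change an improvement

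*SAP*

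**What the plan says.** SAP 3.2.14 describes 30 items, each rated 0 to 5, and states that a higher raw rating is worse. It then turns the scale round. Each subscale is the mean of its items when "all item responses are reverse-coded such that a higher score represents a better disease-specific quality of life", and the summary score is the mean of the subscales. The section closes with: "CFB will be calculated for Visits 2 (Week 4), 3 (Week 8), and 4 (Week 12). A negative CFB reflects improvement".

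SAP 3.2 sets one formula for all endpoints: "Change from baseline is calculated for each endpoint as" the value at the visit minus the value at baseline.

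Two other ranked endpoints are also higher-is-better. For CSBM, SAP 3.2.9 says: "An increase (positive value) reflects improvement". For SE-ADL, SAP 3.2.11 says: "A positive value of CFB reflects improvement".

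On reporting, SAP 4.2.3 says: "Descriptive statistics for each endpoint will be presented as change from baseline by treatment group and visit". For the model-based comparison it adds: "Only the LS means for Week 12 will be used for statistical comparison".

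**The concern.** On a score where higher is better, with change taken as visit minus baseline, a negative change is a deterioration. The closing sentence of 3.2.14 says the opposite, so the SAP gives two incompatible rules for reading the same endpoint.

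The SAP is the pre-specified record of which direction counts as favourable, and it overrides the protocol where the two differ (SAP 1). As it stands, it supports either reading. Someone who relies on the closing sentence when writing a table footnote or the report text would describe a fall in gastrointestinal quality of life as a benefit, and a gain as harm.

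There is also a problem of apparent discordance. PAGI-SYM and PAC-QoL (SAP 3.2.12 and 3.2.13) are higher-is-worse and are correctly labelled negative for improvement. A consistent gastrointestinal benefit would give negative changes on those two and a positive change on PAGI-QoL. Read by the SAP's sentence, PAGI-QoL would seem to contradict the other two.

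**Working it through.** The plan gives no figure to reproduce here, so the check applies the SAP's own rules in order and looks at the sign.

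**Inputs**
- Raw item range 0 to 5, higher is worse (SAP 3.2.14).
- Items reversed, subscale = mean of items, summary = mean of 5 subscales (SAP 3.2.14).
- Change = visit minus baseline (SAP 3.2).
- Assumption: reversed item = 5 - raw, the usual reversal of a 0-5 item. The SAP gives no formula.

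**Sign of the change**

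The mean of (5 - raw) is 5 minus the mean of raw, within each subscale and again across subscales. With complete items, summary = 5 - (mean of the raw subscale means), so change in summary = -(change in the raw mean). The sign is reversed for any non-zero change, not only when all items move together. Starting with every item at raw 2 (summary 3.0):

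| All items move to | Meaning | Summary at visit | Change | Label under the closing sentence |
|---|---|---|---|---|
| 1 | better | 4.0 | +1.0 | not improvement |
| 3 | worse | 2.0 | -1.0 | improvement |
| 5 | worst possible | 0.0 | -3.0 | improvement |

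**Does other text resolve it?**
- Protocol 9.1.10 gives only the raw item rating.
- SAP Table 4-1 (baseline scores) and Table 4-3 (estimands) list PAGI-QoL without a direction.
- SAP 6 (changes to the planned analyses) does not mention it.
- CSBM and SE-ADL are labelled positive for improvement, so the SAP has no general convention that negative is good.

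PAGI-QoL is therefore the only one of the 14 ranked endpoints whose stated direction contradicts its own scoring.

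**Planned output affected**
- Mean changes: 4 groups x 3 visits (Weeks 4, 8, 12) = 12.
- Dose-versus-placebo LS mean differences at Week 12 = 3.
- Total: at least 12 + 3 = 15 signed summaries, planned whether or not the hierarchy reaches this endpoint.

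**Item ranges (minor)**

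SAP 3.2.14 gives diet and food habits 7 items but the range Q13-20, which spans 20 - 13 + 1 = 8, and Q20 appears again under relationship (Q20-22).
- By range: 10 + 2 + 8 + 3 + 8 = 31.
- By stated count: 10 + 2 + 7 + 3 + 8 = 30.

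Suppose the scores were programmed from the ranges, each subscale being the mean of answered items (an assumption). With m of Q13-19 missing and Q20 answered, the size of the shift in the summary is

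|mean of answered Q13-19 - Q20| / (5 x (8 - m)).

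| Difference between the diet mean and Q20 | m = 0 | m = 3 |
|---|---|---|
| 0.5 points | 0.5/40 = 0.0125 | 0.5/25 = 0.02 |
| 5 points (largest possible) | 5/40 = 0.125 | 5/25 = 0.20 |

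A change score with opposite extremes at the two visits doubles the largest values to 0.25 and 0.40. With m = 4, the 7-item version is set to missing (4/7 = 57%, above the 50% limit), while the 8-item version is scored (4/8 = 50%).

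**The case against.** The strongest reply is that no planned calculation depends on the sentence. The MMRM uses the signed scores as they are, and the tests are two-sided at 0.05. The step from one endpoint to the next in SAP 2.4 asks only for a statistically significant difference. An improved/not improved variable is derived only for PGI-S and CGI-S (SAP 4.2.3). PAGI-QoL is ranked last of 14 within each dose, in a trial with no primary efficacy endpoint, and the correct direction is stated a few lines above the wrong one. Also, the closing sentence speaks of change from baseline, so applying it to between-group differences is an inference.

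All of this is accurate, and it limits the point to interpretation. It does not remove it. The signed changes are reported even if the formal test is never reached, and the documents contain nothing that would stop the sentence being carried into footnotes or text. The count of 15 summaries shows where the label would be applied; it does not measure bias, because none of the values change.

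On Q20, the stated counts make the intended split clear and the larger shifts need extreme answers. The general missing-item rule in SAP 2.3.5 could seem to compete with the averaging assumed above, but it applies only where nothing else is specified, and 3.2.14 sets its own 50% rule. The overlap is a drafting slip with a small possible effect.

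**Conclusion.** The contradiction is real and should be fixed. Under the SAP's stated scoring and change formula, the closing sentence of 3.2.14 has the direction of benefit reversed for every non-zero change in PAGI-QoL. It concerns 1 of 14 ranked endpoints and at least 15 signed summaries. The consequence is misreading only: estimates, intervals, p-values and the testing sequence stand.

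The sign result needs only that reverse-coding does what 3.2.14 says it does; the worked values assume 5 minus raw. The documents alone cannot show whether the scoring text or the direction sentence is the one in error. The Q20 overlap is minor and matters only if scores are programmed from the ranges instead of the counts.

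**What to change.** Before unblinding, check 3.2.14 against the instrument's scoring instructions, for both the direction and the item-to-subscale allocation.

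- If reverse-coding is confirmed, change the last sentence to say that a positive change from baseline reflects improvement.
- If the instructions do not reverse-code, correct the scoring text and keep the sentence.
- Set the diet and food habits range to Q13-19. This is the only range that fits the stated 7 items, the total of 30 and the other four ranges.
- Make the same corrections in the programming specification.

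The cost is one check of the scoring instructions, two wording edits in the SAP and the matching specification lines. Data collection, sample size, model and testing order are untouched.

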## 3.3 EXPLORATORY ENDPOINTS

### 3.3.1 Phosphorylated alpha-synuclein aggregates

Skin biopsy will be collected at Visit 1 (baseline), Visit 2 (Week 4), and Visit 4 (Week 12) from participants at select sites. CSF samples will be collected at Visit 1 (baseline) and Visit 4 (Week 12). No statistical assessment will be done for these measures.

## 3.4 SAFETY ENDPOINTS

The primary objective of the study is to assess safety and tolerability of three doses of IKT-148009 in participants with PD, as described in [Section 3.4.2.2](#).

Tolerability is defined as the proportion of participants who discontinue the assigned regimen, and will be reported for the Safety Set.

The safety and tolerability will be assessed descriptively based on an overall evaluation of the following endpoints:

- Incidence and of TEAEs, evaluated by severity/intensity, seriousness, and relationship to study intervention
- Incidence of related TEAEs (including possibly- and probably-related TEAEs) of moderate or severe intensity

- Incidence of TEAEs leading to withdrawal of study drug
- Incidence of serious adverse events (SAEs), including suicidality as measured by the C-SSRS
- Changes in physical examination, vital signs (blood pressure, heart rate, respiratory rate, and temperature), 12-lead ECG, and laboratory data (hematology and blood chemistry)
- Proportion of those randomized in each dosing cohort who discontinue the assigned regimen

Safety analysis is described further in [Section 4.3](#). Safety endpoints will be summarized with descriptive statistics.

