2.2. Background

Despite the success of anti-parkinsonian therapies for motor features of the disease, no intervention has been discovered that adequately controls the non-dopamine features of the illness, and no therapy has been demonstrated to slow or stop clinical progression in PD. These remain major unmet medical needs.

Inhibikase Therapeutics Inc, is developing IkT-148009, a novel and potent inhibitor of the wild type c-Abl tyrosine kinase enzyme, for the treatment of PD. IkT-148009 is a chemical derivative of the anti-cancer agent imatinib (marketed as Gleevec®) with much higher potency for c-Abl kinase inhibition and greater likelihood of brain accumulation leading to effective c-Abl inhibition. IkT-148009 will be administered as powder in capsule.

A detailed description of the chemistry, pharmacology, efficacy and safety of IkT-148009 is provided in the Investigator's Brochure (IB).

3. Objectives and Endpoints

Primary Objective	Primary Endpoints
To assess the safety and tolerability of three IkT-148009 doses in Parkinson's Disease	
 Incidence and temporal profile of treatment-emergent adverse events (TEAEs) evaluated by type/nature, severity/intensity, seriousness, and relationship to study intervention Proportion of those randomized in each dosing cohort who discontinued the assigned regimen
Secondary Objectives	Secondary Endpoints
To evaluate the effects of three IkT-148009 doses on Parkinson's Disease motor features, non-motor features, measures of function, and quality of life	
Change from Baseline to Week 12 in the following outcomes, arranged in hierarchical order:
 
 Movement Disorder Society-sponsored revision of the Unified

Parkinson's Disease Rating Scale (MDS-UPDRS) Parts II + III

- Patient Global Impression-Severity (PGI-S)
- Clinician Global Impression of Severity (CGI-S)
- MDS-UPDRS Part II
- MDS-UPDRS Part III
- MDS-UPDRS Part I
- Non-Motor Symptom Scale (NMSS)
- Complete Spontaneous Bowel Movement score (CSBM)
- ESS (Epworth Sleepiness Scale)
- Schwab and England Activities of Daily Living (SE-ADL) Scale
- Parkinson's Disease Questionnaire (PDQ-39)
- Patient Assessment of Upper Gastrointestinal Disorders Severity Index (PAGI-SYM)
- Patient Assessment of Constipation Quality of Life (PAC-QoL)
- Patient Assessment of Gastrointestinal Disorders Severity Quality of Life (PAGI-QoL)

Exploratory

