5.4.2. Primary Endpoint Analysis

The primary objective is to assess the safety and tolerability of IkT-148009.

The safety and tolerability will be assessed descriptively based on an overall evaluation of the following endpoints:

- Incidence and temporal profile of TEAEs, evaluated by type/nature, severity/intensity, seriousness, and relationship to study intervention
- Incidence of related TEAEs (including possibly- and probably-related TEAEs) of moderate or severe intensity

- Incidence of TEAEs leading to withdrawal of study drug
- Incidence of serious adverse events (SAEs), including suicidality as measured by the C-SSRS
- Changes in physical examination, vital signs (blood pressure, heart rate, respiratory rate, and temperature), 12-lead ECG, and laboratory data (hematology and blood chemistry)
- Safety analysis is described further in Section 5.4.3. Safety endpoints will be summarized with descriptive statistics.
- Proportion of those randomized in each dosing cohort who discontinue the assigned regimen

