### 1.2 STUDY ENDPOINTS

#### 1.2.1 Primary Safety Endpoints

The primary safety endpoints are:

- Incidence of treatment-emergent adverse events (TEAEs) evaluated by severity/intensity, seriousness, and relationship to study intervention
- Proportion of those randomized in each dosing cohort who discontinued the assigned regimen

Other safety endpoints include adverse events (AEs), laboratory parameters, physical examination, vital signs, Columbia Suicide Severity Scale (C-SSRS), and 12-lead ECG measurements.

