### 2.3.2 Study Day

Study Day will be calculated from the reference start date and will be used to show start/stop day of assessments and events.

Reference start date (Day 1) is defined as the day of first administration of study intervention.

- Study Day = (date of event – reference start date +1) if the event date is on or later than reference start date
- Study Day = (date of event – reference start date) if the event date is earlier than reference start date

There is no Study Day 0. In the situation where the event date is partial or missing, Study Day, and any corresponding durations will appear partial or missing in the listings.

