### 4.3 SAFETY ANALYSIS

All safety assessments will be performed on the Safety Analysis. Safety data presented by treatment group will be summarized on an ‘as treated’ basis. Safety variables include treatment-emergent adverse events (TEAEs), clinical laboratory parameters, vital signs, 12-lead ECG results, ophthalmic exams, suicidality, and extent of exposure. Study Day 1 for all safety analyses is defined as the date of the first dose of study drug. Safety and tolerability endpoints will be assessed at Week 12. Tolerability will be assessed by

comparing percentages of premature drug and study discontinuations in the treatment.

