#### 4.3.2 Adverse Events

Treatment emergent adverse events (TEAEs) are defined as those that start or worsen after the first dose of study intervention until the Safety follow-up visit is completed. Safety assessments will include TEAEs tabulated by treatment group; descriptive statistics for continuous variables and frequency counts for discrete variables. No inferential statistical analysis is planned for safety data.

TEAEs will be summarized by treatment group. The incidence of TEAEs will be reported as the number (percent) of participants with TEAEs within system organ class (SOC) and preferred term (PT). Participants will be counted only once within a SOC and PT, even if the participant experienced more than one TEAE within a specific SOC and PT.

TEAEs will also be summarized by dose group, SOC and PT for the following:

1. By maximum severity
2. By relationship to study drug
3. By seriousness
4. Related TEAEs of moderate or severe intensity
5. Leading to withdrawal of study drug
6. Serious Adverse Events (SAE)
7. Suicidality as measured by the C-SSRSSafety and tolerability endpoints will be summarized for the end of the week-12 placebo-controlled study.

Supportive listings will be provided for each summary table. The AE listing will include day of onset and end day.

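### The SAP leaves temporal profile out of the protocol's first primary endpoint without declaring the change, and plans no by-arm summary of when TEAEs occur

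*SAP*

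**What the plan says.** **Protocol.** Section 3 (Objectives and Endpoints) gives the first primary endpoint as "Incidence and temporal profile of treatment-emergent adverse events (TEAEs) evaluated by type/nature, severity/intensity, seriousness, and relationship to study intervention". The synopsis says the same. Section 5.4.2 repeats it among the items on which safety and tolerability will be judged descriptively: "Incidence and temporal profile of TEAEs, evaluated by type/nature, severity/intensity, seriousness, and relationship to study intervention".

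**SAP endpoint definitions.** Section 1.2.1 has "Incidence of treatment-emergent adverse events (TEAEs) evaluated by severity/intensity, seriousness, and relationship to study intervention". Section 3.4 has "Incidence and of TEAEs, evaluated by severity/intensity, seriousness, and relationship to study intervention", and ends by committing to a descriptive summary of the safety endpoints.

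**SAP analyses.** Section 4.3 states that "Safety and tolerability endpoints will be assessed at Week 12". Section 4.3.2 plans the number and percentage of participants with TEAEs by system organ class and preferred term, then seven further breakdowns. On timing it says only that "The AE listing will include day of onset and end day". Section 2.3.2 defines Study Day, which "will be used to show start/stop day of assessments and events".

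**Precedence and declared changes.** SAP Section 1 makes the SAP decisive where it differs from the protocol, and Protocol 5.4.1 agrees. Protocol 5.4.1 adds that a major SAP change will be carried into a protocol amendment. SAP Section 6 declares the new mITT definition, the added FAS and the changed testing order. It says nothing about the TEAE endpoint.

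**The concern.** Safety and tolerability by dose is the trial's primary objective, and Protocol 4.2 includes finding a minimum safe dose and a maximum safe tolerated dose among the aims. For that purpose it matters whether events cluster in the first weeks and settle, or build up with continued dosing, and whether this differs between 50, 100 and 200 mg. A count of participants with at least one event over the whole period cannot tell these patterns apart.

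The TEAE window in SAP 3.4.2 runs from first dose to the safety follow-up or early termination visit. Each percentage therefore pools events on drug with events after the last dose. For a completer, the period after treatment is the 14 days between the scheduled Day 85 and Day 99 visits. For someone who stops drug early but stays in the study it is longer.

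**Working it through.** No figure in the plan bears on this point, so the check is a comparison of text.

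**1. Where the component is named.**

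| Place | Incidence | Temporal profile | Type/nature |
|---|---|---|---|
| Protocol synopsis | yes | yes | yes |
| Protocol Section 3 | yes | yes | yes |
| Protocol 5.4.2 | yes | yes | yes |
| SAP 1.2.1 | yes | no | no |
| SAP 3.4 | yes | no (stray *and* before *of*) | no |

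All three protocol statements name temporal profile; neither SAP statement does. SAP 1.2.1 is a complete sentence without it, so the gap is not only the broken phrase in 3.4.

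**2. Whether an SAP analysis supplies it anyway.** The seven breakdowns in SAP 4.3.2 are maximum severity, relationship, seriousness, related events of moderate or severe intensity, events leading to withdrawal of study drug, SAEs, and suicidality. None uses onset interval, visit, time to onset or duration. Each participant counts once within a class and term (SAP 3.4.2 and 4.3.2), so the tables carry no timing. By contrast, *type/nature*, which also left the SAP wording, is still covered by the organ class and preferred term tables.

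**3. What timing information remains.** Onset and end day appear in the listing, Study Day is derived, and Appendix 8.1 gives rules for partial onset dates. Timing is thus collected, derived and shown for each participant, but not summarised by arm. A listing does not meet the commitment in SAP 3.4 to summarise safety endpoints descriptively.

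**4. Whether the change is declared.** SAP Section 6 does not mention it.

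**5. Whether the protocol specified a method.** It did not. Protocol 5.4.5 lists frequency counts and breakdowns that SAP 4.3.2 largely reproduces. Protocol Section 5 leaves the more detailed description of the analyses to the SAP.

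**The case against.** The best defence is that nothing specified was removed. The protocol names temporal profile but attaches no analysis to it, asks only for an overall descriptive assessment, and tests no safety hypothesis. Timing is still reported by participant. Related outputs are planned by arm: time on treatment and total dose (SAP 4.3.1), discontinuation with reasons (4.1.1) and for the Safety Set (4.2.2), laboratory shifts at each post-baseline visit (4.3.4), and vital signs by visit (4.3.5.1). Section 6 is also headed as a list of major changes, and whether this one is major can be argued.

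Most of this stands, and it limits the point. It does not remove it, because none of these outputs shows when TEAEs occur in each arm.

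Three stronger readings are tempting, but the documents do not support them:

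- *Half of the primary endpoint is never analysed.* The documents give the components no weights, the onset and end-day listing exists, and the discontinuation endpoint is retained.
- *The sponsor removed the term on purpose.* The broken phrase in 3.4 fits an unfinished edit as well as a decision, and the documents do not say which.
- *Early stopping distorts the percentages by a known amount.* One could take the 10% drop-out in SAP 1.3.3, get 0.10 × 30 = 3 participants per arm, and suppose that each stops at Week 4 of 12. But that 10% is an assumption for the power of MDS-UPDRS Parts II + III, and the Week 4 stop appears nowhere. Participants who stop drug are encouraged to stay for evaluation (Protocol 8.1), and adverse events are collected until the follow-up visit (Protocol 9.3.1). The example measures no bias.

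**Conclusion.** The point holds as an undeclared omission with a small reporting consequence. Followed as written, the SAP leaves one of the two named components of the first primary endpoint without any summary by treatment group, and timing appears only in a participant-level listing. It drops a named component, not an analysis that the protocol had laid out.

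The effect cannot be put as a number: no test, sample size or error rate depends on it, and the underlying data are not lost. The conclusion rests on two readings: that the SAP governs, as both documents say, and that a listing is not a descriptive summary. It does not depend on why the words are missing. An editing slip needs correcting, and a deliberate change needs declaring. The sponsor should act because this is a primary endpoint and the remedy is cheap.

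**What to change.** 1. Restore *temporal profile* in SAP 1.2.1 and 3.4, and complete the broken phrase in 3.4.
2. Add to SAP 4.3.2 one descriptive table by treatment group of TEAEs by onset interval, with the number of participants at risk in each. Suitable intervals are Day 1 to Week 4, Weeks 4–8, Weeks 8–12, and after last dose. Set the day limits so that they do not overlap, and define the last category from each participant's own last dose.
3. Footnote the number of imputed onset dates. Appendix 8.1 sets a partial onset date in the same month (or, if the month is also missing, the same year) as first treatment to the day of first treatment, which moves such events into the first interval.
4. If the removal was intended, declare and justify it in SAP Section 6 instead. If the SAP can no longer be amended before unblinding, state the change in the clinical study report.

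Kaplan-Meier summaries of time to first TEAE are optional; the protocol does not ask for them. The cost is one extra table from data already collected and listed.
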